9.6. Responsibilities of the sponsor

9.6.1. SAE Recording and assessment

The sponsor shall keep detailed records of all SAEs which are reported to him by investigators.

The sponsor is responsible for the assessment of the causality of the SAE in relation to the NPA collection. In the absence of information on causality from the reporting investigator, the sponsor should consult the reporting investigator and encourage him to express an opinion on this aspect. The causality assessment given by the investigator should not be downgraded by the sponsor. If the sponsor disagrees with the investigator's causality assessment, the opinion of both the investigator and the sponsor should be provided in the report to the National Competent Authority.

All SAE for which the investigator or the sponsor considers that a causal relationship is a reasonable possibility are considered as suspected Serious Adverse Reaction (SAR).

The expectedness of the SAR shall be determined by the sponsor. The sponsor assesses if the SAE is expected or not using information described in the protocol (section 9.2), especially concerning, acts and methods performed for the research. An unexpected adverse reaction is an adverse reaction, the nature, the outcome or severity of which is not consistent with this information.

9.6.2. New fact reporting

When a new event is likely to affect the safety of participants, the sponsor and the investigator take appropriate urgent safety measures to protect participants against any immediate hazard.

The sponsor inform without delay the Competent Regulatory Authorities of safety data that may be relevant in terms of subject safety, or safety issues which might alter the current benefit-risk assessment of the study.

The Inserm Pharmacovigilance department shall transmit a written report to the Competent Regulatory Authorities and concerned Ethic Committee.

10. DATA COLLECTION AND PROCESSING

10.1. Description of data collected

10.1.1. Individual patient data

Once enrolled in the study, the following data will be collected for each patient by study nurses and/or site investigators, on remote data capture devices:

- Individual identifiers: month and year of birth, sex
- Anthropometric and clinical data: weight, height, vital signs, symptoms, treatments and adherence, AEs
- Data on the tolerability of NPA collection (qualitative and quantitative)
- Radiological and ultrasonography data: digital images and interpretation
- Laboratory data: mycobacterial culture and Ultra assay, blood tests
- Samples collected for biobanking
- TB treatment, if initiated
- Comorbidity management: antiretroviral treatment, treatment of other opportunistic infections, other
- Outcome data: end of study status or early study termination (death, lost to follow-up, withdrawal)

For each new patient included in the study, an anonymised individual identification code will be attributed and used as the only patient identifier in the REDCap database.

10.1.2. Cost data

We will collect data to estimate the costs of the TB diagnostic approaches being compared. This will include the costs of TB diagnostics, including collection and testing of samples, and the other direct health costs required to treat patients, including treatment for HIV, TB and other comorbidities, use of equipment and staffing costs.

We will measure and record, or where necessary estimate, resource utilization for both use of the PAANTHER TB treatment decision algorithm and for standard of care in children with HIV. Unit costs will be collected from relevant sources including clinic and hospital site visits, accounts and invoices from the TB-Speed project and individual facilities, pharmaceutical and medical equipment manufacturers, Ministries of Health and NTPs.

To estimate human labour costs, we will conduct a time and motion study survey to estimate quantities of staff time involved in different health care tasks. To do so, we will ask nurses, doctors and other health workers participating in this study to self-complete timesheets recording the length of time they spend conducting each task.

Costs will be expressed in U.S. dollars, converted using purchasing power parity exchange rates, i.e. market exchange rates adjusted for differences in purchasing power between countries.

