11.2.4. Cost-effectiveness analyses

A mathematical model will be informed by the data collected during the trial and costs from a specific survey to project mortality and costs for the following strategies: 1) the standard of care with current TB diagnostics practice in children with HIV; 2) the TB-Speed approach using the PAANTHER TB treatment decision algorithm with improved and active TB diagnostics. The projected mortality will be used to estimate Disability Adjusted Life Years saved (DALYs) for each strategy. ICERs will compare the differences in DALYs and costs between the 2 strategies. ICERs will be estimated for each country separately and will be compared to previously published estimated cost-effectiveness thresholds for each country.

The cost-effectiveness analysis will be from the health payer perspective and only direct health care costs will be included. A budget impact analysis will be conducted to evaluate the actual impact of implementing the new TB-Speed approach on health care budgets at 2- and 5-year horizons in the countries participating in the project.

Sensitivity analyses will be conducted to assess uncertainties around the estimates and the robustness of our findings. Variation of parameters such as TB prevalence, TB incidence and

costs will help to simulate different scenarios of implementing the TB-Speed approach, adapted to the countries' specific contexts. The latter will be important for the generalization of the results and to inform more general TB guidelines.

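### Costs labelled as U.S. dollars are to be converted at purchasing-power-parity rates, so the budget impact will not show payer spending, and nothing ties the ICERs to the unit of their thresholds

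*Protocol*

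**What the plan says.** Section 10.1.2 of the protocol states the conversion rule in one sentence: "Costs will be expressed in U.S. dollars, converted using purchasing power parity exchange rates". It explains PPP rates as market rates adjusted for purchasing power and names no exception. Unit costs are to come from site visits and from "accounts and invoices from the TB-Speed project and individual facilities, pharmaceutical and medical equipment manufacturers, Ministries of Health and NTPs".

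Section 11.2.4 sets out how the costs will be used:

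- On perspective: "The cost-effectiveness analysis will be from the health payer perspective and only direct health care costs will be included".
- On the decision rule: "ICERs will be estimated for each country separately and will be compared to previously published estimated cost-effectiveness thresholds for each country". The currency and price year of those thresholds are not given.
- On budgets: "A budget impact analysis will be conducted to evaluate the actual impact of implementing the new TB-Speed approach on health care budgets", at horizons of 2 and 5 years in the participating countries.

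Section 4.5 repeats the payer perspective and the budget aim, and says the work should guide health authorities' decisions. It defers the economic analysis to a separate plan, which is not at hand, and refers to 10.1.2 for how cost data are collected.

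**The concern.** There are two problems, and the first is firmer.

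**Budget impact.** A health budget is spent in local currency, or in dollars bought at the market rate. A PPP-converted amount answers a different question: what the same bundle would cost at a common price level. It is not an outlay. The protocol applies the PPP rule to all costs and also promises a figure for the effect on real budgets. Both cannot be met by the same number. Calling the result U.S. dollars makes it easy for a ministry or funder to read it as money to be found.

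**ICER against threshold.** An ICER can be set against a threshold only when both are in the same unit and price year. The protocol fixes the unit of the ICER as PPP-converted, leaves the unit of the threshold open, and does not ask that the two agree.

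At stake are the usefulness of the budget figures to payers and the validity of the country-level cost-effectiveness conclusions (secondary endpoint 10). The primary analysis of the negative predictive value and the sample size are untouched.

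**Working it through.** The protocol gives no cost figure, exchange rate or threshold, so there is nothing of its own to reproduce. The check is one of units, followed by an illustration.

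**Step 1: units.** Let C be a cost in local currency, M the market rate (local units per U.S. dollar) and P the PPP rate (local units per international dollar).

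- Market-rate value: C / M, in U.S. dollars.
- PPP value: C / P, in international dollars.
- Ratio of the second to the first: r = M / P.

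The two agree only if r = 1. Section 10.1.2 prescribes C / P and gives it the label of C / M.

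**Step 2: compare the rule with its uses.**

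| Use | What it needs | What 10.1.2 supplies |
|---|---|---|
| Budget impact (4.5, 11.2.4) | Local currency or C / M | C / P, no exception stated |
| ICER against country threshold (11.2.4) | Same unit and price year as the threshold | C / P; threshold unit and year not stated |
| Comparison across the four countries | A common price level; C / P is suitable | C / P, labelled as U.S. dollars |

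**Step 3: size, under an assumption.** The value of r is not in the protocol. Assume r = 1.5 to 3. Let s be the share of a cost that is priced in local currency, with the remainder already in U.S. dollars and left as invoiced. The multiplier relative to market dollars is

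f = s × r + (1 − s).

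- s = 1: f = 1.5 to 3.0.
- s = 0.5: f = 0.5 × 1.5 + 0.5 = 1.25, up to 0.5 × 3 + 0.5 = 2.0.

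The second line matters only if some items are invoiced in dollars and are not converted. The protocol does not say whether this is so.

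**Step 4: effect on a threshold comparison.** Suppose the threshold T is in market dollars of the same year. The PPP-converted ICER exceeds T whenever the market-dollar ICER exceeds T / f.

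- All local: 1 / 1.5 = 67% of T, down to 1 / 3 = 33% of T.
- Half local: 1 / 1.25 = 80% of T, down to 1 / 2 = 50% of T.

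An intervention whose market-dollar ICER lies between that cut-off and T would be called not cost-effective only because of the unit. If T is itself in PPP dollars of the same year and all costs are converted alike, the comparison is sound.

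**The case against.** The strongest reply is that the economic analysis has its own plan. Threshold unit, price year, treatment of dollar invoices and budget currency are normal content for it, and section 4.5 points to 10.1.2 only for data collection. That holds for details the protocol leaves open. It does not hold for the conversion rule, which the protocol states outright. A plan that follows the rule inherits the problem, and a plan that avoids it departs from the protocol.

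The second reply is that PPP conversion is a legitimate choice in a four-country study and is disclosed in the same sentence. ICERs are estimated country by country, so a single factor within a country cannot change which strategy costs more or the sign of the ICER. This stands. It means that making market rates primary for the ICER would be partly a matter of preference. It does not rescue the budget impact, where the aim is spending.

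A reader might go further and infer three things that the protocol does not support:

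- That cost-effectiveness verdicts will flip. The thresholds' unit is unknown, and a match is possible.
- That totals will mix two units. The listed sources do not say in which currency they invoice. A dollar price could also be taken to local currency at the market rate and then converted at PPP, which gives one unit throughout.
- That results are wrong by a known multiple. The ratio is an assumption.

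**Conclusion.** The point holds for the budget impact as written: the protocol's only conversion rule yields international dollars under a U.S. dollar label, and no exception is made for an analysis that is meant to show the real effect on budgets. For the ICER the point is conditional. The comparison is valid if thresholds and ICERs share a unit and price year, and the defect is that the protocol does not require this.

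The size rests on an assumed ratio of 1.5 to 3, under which a fully local cost, and the budget impact built on it, would read 1.5 to 3 times the market-dollar value. Whether any cost-effectiveness conclusion would change depends on that ratio and on the threshold unit, neither of which the protocol gives. The sensitivity analyses named in 11.2.4 vary TB prevalence, TB incidence and costs; the conversion basis is not among the parameters named. The change should be made, but it concerns an ancillary analysis only.

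**What to change.** Amend sections 10.1.2 and 11.2.4, and carry the same text into the separate economic plan:

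1. Report the budget impact in local currency, in U.S. dollars at the market exchange rate of a stated price year, or in both.
2. Express each ICER in the same currency unit and price year as the threshold with which it is compared, and state both.
3. Label any PPP-converted result as international dollars. PPP may be kept for comparison across countries.
4. Treat items priced in U.S. dollars in one consistent way within each total, and say which way.

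The cost is a few sentences. Conversion takes place after the costs are collected, so no new data are needed.

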10.2. Definition of source data

Source data must be available to document the existence of patients enrolled in the study and should substantiate integrity of the data collected. It must include the original documents relating to the study, the medical treatments and medical history of the patient.

The following information should be collected from source medical records filled by site physicians:

- Patient's demographic data (month and year of birth, sex)
- Study name(s) and protocol number(s) in which the patient participates
- Details related to the inclusion criteria
- Date of signing informed consent form
- Dates of follow-up visits
- Medical history and physical examination details
- Laboratory print-outs
- AEs and concomitant treatments

For the purpose of the study, specific forms may be developed for source data collection to be inserted into medical records.

In addition to the source medical records, radiological data will be collected as digital imaging and communications files (.dicom files). CXRs interpretation will be directly reported in the patient's CRF using standardized forms developed as part of the capacity building component of the TB-Speed Output 1.

In the same way, Ultra test result files (.gxx files) will be extracted directly from the GeneXpert software.

Data transfer for dicom and gxx files is detailed in Chapter 10.3.6.

10.3. Electronic data entry

The eCRF system, the methods to ensure restricted access to the database, and the data management procedures, including the procedures to check completeness, accuracy, quality and validity of the data, will be described in specific trial SOPs in accordance with good clinical, scientific and data management principles.

10.3.1. eCRF

A real time data collection is needed for optimised monitoring of data entry. No paper CRFs will be used; patient data collected at inclusion and follow-up visits will be recorded directly in an eCRF by study nurses, mostly through single data entry.

The TB-Speed data management system will be based on the electronic data capture application REDCap (Research Electronic Data Capture; https://www.project-redcap.org/). REDCap is an online tool for eCRF development, allowing data input from anywhere in the world over a secure connection with authentication and data logging.

Design and conception of the eCRF will be done by the international trial manager in close collaboration with the international data manager.

10.3.2. Data hosting

The REDCap MySQL database server will be hosted by the international CTU at the University of Bordeaux (UBx), France. REDCap is a free, secure web application for building and managing online surveys and databases, it's geared to support online and offline data capture.

Developed by Vanderbilt University, the REDcap software complies with internationally recognized standards including the Health Insurance Portability and Accountability Act (HIPAA, 1996), the United States legislation providing data privacy and security provisions for safeguarding medical information, as well as part 11 of Title 21 of the Code of Federal Regulations (CFR) that establishes the United States Food and Drug Administration (FDA) regulations on electronic records and electronic signatures.

10.3.3. Data security

The eCRF will be accessible 24/24h by secure authentication to a restricted users group. The connection will be authenticated by a user id, password and digital certificate enabling data encryption during transfer and storage to the central server. Access and rights levels will be granted and managed by the international data manager (international CTU).

The server hosted at UBx will be saved every weekend on a hard drive, and send to bands (rotation frequency of the bands will be every five weeks). The database will be saved incrementally on a hard drive every working days.

10.3.4. Data entry

Field-based users will be able to access REDCap either through a classical Internet-connected tablet or computer, or through the REDCap mobile App application. The mobile App also enables offline data entry through a tablet or an Android mobile phone. In such a case, the tablet or mobile phone will be brought by the Clinical Research Assistant (CRA) to the country CTU and further synchronized with the central database once connected to the Internet (Figure 3).

Tablets will be purchased locally by country CTUs. Configuration of tablets will be managed by the international data manager.

[figure not shown]

Figure 3: Secure data flow

1 Only for GXX et DICOM files 2 For GXX, DICOM and patient data files Main data transfer Optional data transfer in case main data transfer is unavailable

Project Managers from country CTUs will be in charge of training the relevant study staff for data collection and issuing of electronic data queries for QC. The investigator is responsible for ensuring that all sections in the eCRF are completed correctly and that entries can be verified against source data. If the investigator authorizes other persons in their staff to make entries on the eCRF, the names, positions, and signatures must be documented in writing. eCRF must be completed during/after each study visit. Any person entering data in the eCRF must be trained beforehand and appointed to do this task.

10.3.5. Data coding

The Anatomical Therapeutic Chemical (ATC) system will be used for drug classification and coding. As part of safety monitoring, AEs will be coded using the Medical Dictionary for Drug

Regulatory Affairs (MedDRA, version 17.1). Coding will be performed by country CTUs based at TB-Speed consortium members institutions.

10.3.6. Data transfer

Individual patient data will be transferred from tablets to the server located at UBx using a secure file transfer protocol (ftps) with individual authentication and data logging.

CXRs (.dicom files) and Ultra test result files exported from GeneXpert (.gxx files) will be transferred to the international CTU central server using a secure web transfer (ftps). In case implementing sites experience web access issues, transfer of CXRs and Ultra result files will be done 1/ by GSM with a tablet (equipped with a SIM card) from the implementing sites to the country CTU, and 2/ from the country CTU to the international CTU central server via a secure web transfer (ftps).

In the context of the Covid pandemic, due to travel restrictions, remote site monitoring visits might be conducted by the international CTU. Where needed, pseudonymized source documents will be forwarded by the country CRA through a ftps for monitoring purpose only; source documents will be destroyed afterwards.

10.4. Description of the data verification, validation and processing (data management)

A data management plan (DMP) will be established and validated by the study coordination team at UBx. Verification of the completeness and consistency of the data is performed for all key data as well as a list of additional data defined in the DMP.

A data management system (DMS) will be developed at UBx to enable generation of standardized lists of data management queries at country level. Queries will be programmed for data completeness, integrity and consistency as defined in the DMP. They will be run on an at least monthly basis at the country level. Data management checks will be implemented at central level on a monthly basis. If needed, centralized correction queries will be sent by the international coordinating CTU to the country CTU, and by the country CTU to study sites. At country level, queries will be managed by the country data manager or CRA. Queries will be solved by data managers along with the country CRA.

The investigator, co-investigators, head of laboratory must allow access to relevant hospital, laboratory or clinical records, to confirm their consistency with the CRF entries. All research staff working in the study, including study nurses, national CTU team (PMs, CRAs), PIs, international coordination team (CRA, Trial Manager, Coordinating Investigators) will sign a confidentiality agreement with regards to access to individual patient data and medical records.

Central statistical monitoring will also be implemented by the international coordinating CTU to look at variables for which distributions differ from the rest of the observed data at the country, site or patient level. Its purpose is to highlight systematic (non-random) faults in filling the CRF data, protocol compliance, AEs, and to guide targeted monitoring. Variables subject to statistical monitoring are specified in the monitoring plan. Comparison of distributions is made by statistical tests or models.

Before database freezing, a final data review will be conducted by the international data manager and remaining issues will be adjudicated. Closure of the database will be performed by the international data manager.

10.5. Lenght of data retention, archiving conditions and management

All data will be stored in a server hosted by the CREDIM (*Centre de Recherche et Développement en Informatique Médicale*) at UBx and will be declared to the French data protection authority CNIL (*Commission Nationale de l'Informatique et des Libertés*) in accordance with French regulations on personal data protection.

The server is located in a secure computer room. The network is protected by uninterrupted power supply firewalls and up-to-date viruses and malwares scanning softwares. Data

backups are performed regularly. Reading, entry, modification or deletion of data will be granted via the standard authentication and access-control features.

Medical records will be stored in the clinical sites as per standard practices. Electronic data and files will be maintained on password-protected computers. Essential study documents will be retained at the coordinating centre for fifteen years after study completion.

No displacement or destruction of data will be done without the agreement of the sponsor. At the end of the regulatory archiving period, the sponsor will be consulted for destruction.

10.6. Study documents archiving conditions and management

Essential documents and study records will be kept secured fifteen years after study completion, under the responsibility of each country investigator, the international CTU, and the sponsor.

Study documents constituting the Trial Master File (TMF) will be made available online to investigators on a secured website. The international coordinating CTU will be responsible for routinely updating global documentation on the study website. Country CTUs will be responsible for routinely updating national documentation on the study website.

Investigators will ensure that study records are not disposed of or removed from the study sites or the country CTU without prior notification and approval from the sponsor or his representative.

Each investigator will keep a hard copy of original documents whenever those are manually signed or generated. This includes, at site level, medical records (source documents) and study ID assignment log which are subjected to professional secrecy and confidentiality, and task delegation lists.

Data, documents, reports and SOPs should be available to be audited or inspected at any time.

